2.2 Secondary Objectives

- Does tumor location impact the influence of tumor: breast ratio on patient reported outcomes following mastectomy with reconstruction or BCT?
- How does the pre and post-op Breast Q for the two groups (mastectomy + recon vs. BCT) reflect the tumor: breast ratio as calculated from 3D images rendered from MRI utilizing software-based algorithms?
- How does the pre and post-op Breast Q for the two groups (mastectomy + recon vs. BCT) reflect the VECTRA 3D generated mammometrics?

- What is the impact of radiation in BCT on Breast Q (Q-score before and after radiotherapy) and VECTRA (breast volume, nipple position, total breast skin surface area before and after radiotherapy)?
- How do complications that arise from each scenario (mastectomy + recon) vs. BCT impact patient satisfaction?
- What is the impact of tumor location and obesity as independent determinants of patient satisfaction in the two groups (mastectomy + recon vs. BCT) relative to tumor: breast ratio?

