6.5 Visits #4 - 5: Post-Operative Visits

All patients will have routine follow up visits after surgery. Timing of follow-up will be variable among the three groups.

- **Group A:** The surgical oncologist will see the BCT group.
 - Post-Lumpectomy 1st Post-op Visit before Radiotherapy (*1-10 weeks after lumpectomy*)
 - Post-Op Breast Q will be administered and routine imaging taken to quantify volume and mammometric parameters

- Post-Lumpectomy Post-op Visit after Radiotherapy (*6- 18 months after radiation or the latest follow-up time point within the duration confines of our study period.*)
 - Post-Op Breast Q will be administered and routine imaging taken to quantify volume and mammometric parameters

Some patients will require no adjuvant chemotherapy following lumpectomy based on their pathology. These patients are typically radiated 4-10 weeks after lumpectomy. Other patients will require chemotherapy after lumpectomy but prior to radiation. Chemotherapy duration can vary depending on selected treatment regimen but can be between 8-18 weeks excluding Herceptin which typically is administered every 6 weeks for 1 year. Patients receive Herceptin during radiation and reconstruction and so the administration of Herceptin does not independently alter any study time points. Patients will not undergo chemotherapy or radiation until after re-excision is performed in cases where there is a positive cancer margin after lumpectomy per standard of care.

[figure not shown]
- **Group B:** Mastectomy with reconstruction patients will be seen in follow up with plastic surgery.
 - Post-mastectomy 1st Post-op Visit before Completion of Reconstruction (*1-10 weeks after mastectomy*)
 - Post-Op Breast Q will be administered and routine imaging taken to quantify volume and mammometric parameters
 - Post-mastectomy Post-op Visit after Final Reconstruction (*3-8months after final reconstructive procedure or the latest follow-up time point within the duration confines of our study period.*)
 - Post-Op Breast Q will be administered and routine imaging taken to quantify volume and mammometric parameters
- **Group C:** The surgical oncologist will see the mastectomy only group.
 - Post-mastectomy 1st Post-op Visit (*1-10 weeks after mastectomy*)
 - Post-Op Breast Q will be administered and routine imaging taken to quantify volume and mammometric parameters

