6.6 Variable Duration of Study Observation

Some patients may receive neoadjuvant chemotherapy prior to either lumpectomy or mastectomy. Adjuvant chemotherapy may also be required based on pathologic findings. If required, chemotherapy may begin approximately 6 weeks following surgery. Chemotherapy

duration can vary depending on selected agents but can be between 8-18 weeks. Radiotherapy if needed is usually scheduled for 6 weeks after the final chemotherapy and can last approximately 6 weeks. Treatment time may be lengthened for complications. Reconstruction procedures can happen in multiple stages, therefor extending the time to final completion. This variability in adjuvant treatment will affect the timelines for follow-up and will be recorded for study purposes.

Fig. 1. Study Arms and Duration

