Does tumor location impact the influence of tumor: breast ratio on patient reported outcomes following mastectomy with reconstruction or BCT?

- Add location and three way interaction term –group-by-T:B ratio-by-location into Model 2 – (Model 3). The results can be better presented as two graphs – one for each location. See Model 2 for the graph.

How does the pre and post-op Breast Q for the two groups (mastectomy + recon vs. BCT) reflect the tumor: breast ratio as calculated from 3D images rendered from MRI utilizing software-based algorithms?

- Fit and test a model with Q-score as the dependent variable and 3D image data as the independent variable with appropriate non-linear terms for 3D (e.g. spline functions), with group and possible interaction of group-by-3D (Model 4).

How does the pre and post-op Breast Q for the two groups (mastectomy + recon vs. BCT) reflect the VECTRA 3D generated mammometrics?

- Both the Breast Q and the VECTRA 3 D generated mammometrics are continuous variables. The correlation between them will be quantified by Pearson or Spearman correlation coefficient with one sample t test for population correlation coefficient =0, and with Fisher Z transformation to test the population correlation coefficient not equal to zero.

What is the impact of radiation in BCT on Breast Q (Q-score before and after

radiotherapy) and VECTRA (breast volume, nipple position, total breast skin surface area before and after radiotherapy)?

- Perform the subgroup analyses of BCT patients comparing change in outcomes of interest before and after radiation.

How do complications that arise from each scenario (mastectomy + recon) vs. BCT impact patient satisfaction?

- Fit and test a model with Q-score as the dependent variable and complication and group, and possible group-by-complication interaction as independent variables controlling for W in the model.

What is the impact of tumor location and obesity as independent determinants of patient satisfaction in the two groups (mastectomy + recon vs. BCT) relative to tumor: breast ratio?

- Fit and test a model with Q-score as the dependent variable and group, T:B ratio, location, and obesity as the independent variables, controlling for W in the model. Obtain the standardized regression coefficients for location, obesity, and T:B ratio, and compare each other to determine their relative importance.

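### The before/after change in BCT patients cannot separate radiation from surgical recovery and interval chemotherapy, so it should not be concluded as the impact of radiation

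*Combined protocol and SAP*

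**What the plan says.** The objective in section 2.2 reads "What is the impact of radiation in BCT on Breast Q (Q-score before and after radiotherapy" and continues with VECTRA breast volume, nipple position and skin surface area. The matching analysis in section 10.5.2 is one sentence: "Perform the subgroup analyses of BCT patients comparing change in outcomes of interest before and after radiation". It names no comparator, test, covariate, chemotherapy term or time term.

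Section 6.5 sets the two measurements for Group A. The earlier is the "Post-Lumpectomy 1st Post-op Visit before Radiotherapy", 1-10 weeks after surgery (Appendix A adds that margins must be clear). The later is "6- 18 months after radiation or the latest follow-up time point within the duration confines of our study period". On what happens in between, section 6.5 says of patients without chemotherapy: "These patients are typically radiated 4-10 weeks after lumpectomy". It then adds: "Other patients will require chemotherapy after lumpectomy but prior to radiation". Section 6.6 gives the timing: "chemotherapy may begin approximately 6 weeks following surgery", and its "duration can vary depending on selected agents but can be between 8-18 weeks". The same section puts radiotherapy about 6 weeks after the last chemotherapy, for about 6 weeks.

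Section 1.1 defines BCT as lumpectomy with radiation, and Appendix A labels Group A as BCT + XRT. Section 10.3 includes the mastectomy-only patients as a control for reconstruction, not for radiation.

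**The concern.** A before/after change measures the effect of an exposure only if nothing else of consequence changes between the two measurements. Here the first is taken while the patient is recovering from surgery and the second many months later. Recovery lies in that interval for every patient, and chemotherapy for some. Reporting the whole change as the impact of radiation credits one cause with the net result of several.

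The error could run either way. Improving scores as the patient recovers could hide a harm of radiation or look like a benefit. Loss of volume as post-operative swelling resolves could be read as radiation shrinkage. The study is meant to inform the choice between BCT and mastectomy with reconstruction, so a statement about what radiation does to satisfaction or breast shape may be relied on.

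**Working it through.** **1. The plan's own figure.** The radiation objective has no sample-size figure. The only one is 83 per arm (section 10.4), for the between-group comparison with d = 0.45, two-sided 0.05 and 80% power. The normal formula gives 2(1.960 + 0.842)²/0.45² = 77.5, so 78. The two-sample t-test gives 79. The Wilcoxon version with a normal parent (relative efficiency 3/π) gives 83. The figure therefore reproduces under that test, which the plan does not name. It is used below only as the planned number of BCT patients.

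**2. Length of the interval**, in weeks from lumpectomy, taking 6 months as 26 weeks, 18 months as 78 weeks and a 6-week radiation course. Visit 4 is capped at the start of radiation because the protocol places it before radiotherapy.

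| | Radiation starts | Radiation ends | Shortest Visit 4 to Visit 5 gap | Longest gap |
|---|---|---|---|---|
| No chemotherapy | 4 to 10 | 10 to 16 | (10 + 26) − 4 = 32 | (16 + 78) − 1 = 93 |
| Chemotherapy | 6 + 8 + 6 = 20 to 6 + 18 + 6 = 30 | 26 to 36 | (26 + 26) − 10 = 42 | (36 + 78) − 1 = 113 |

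The radiation course takes up 6/93 to 6/32 (6-19%) of the gap without chemotherapy and 6/113 to 6/42 (5-14%) with it. These are shares of time, not of effect. The last-available-follow-up clause can move the later visit outside these limits. Chemotherapy may start at about week 6 and Visit 4 may be as late as week 10, so some earlier values may already be taken during chemotherapy.

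**3. What the arm can identify.** Let H be the change from recovery and elapsed time, R that from radiation and K that from chemotherapy.

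- Mean change without interval chemotherapy: H + R.
- Mean change with it: H + R + K.

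The difference gives K, provided the two subsets are otherwise alike (their intervals differ, as step 2 shows). No contrast within an arm where everyone is irradiated separates H from R.

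**4. Which covariates matter.** For patient i with covariates x that do not vary between visits (chemotherapy yes/no, weeks to Visit 4, baseline score):

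- Visit 4: Y = a + g·x + b_i + e₄
- Visit 5: Y = a + v + g·x + b_i + e₅
- Difference: v + (e₅ − e₄)

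The g·x term cancels. With both visits observed, main effects leave v equal to the raw mean paired change. Only visit-by-covariate interactions alter it.

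**5. Illustration of consequence.** Assume R = 0, 83 patients with both visits, a paired t-test at two-sided 0.05, and the plan's SD of 20. The before/after correlation r is not in the documents; 0.3 to 0.7 is assumed. SD of change = 20√(2(1 − r)): 23.7, 20.0 and 15.5. At r = 0.5 the standard error is 20/√83 = 2.195, so a 5-point shift has noncentrality 5/2.195 = 2.28.

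| Assumed non-radiation shift | r = 0.3 | r = 0.5 | r = 0.7 |
|---|---|---|---|
| 3 points | 0.21 | 0.27 | 0.41 |
| 5 points | 0.48 | 0.61 | 0.83 |
| 10 points | 0.97 | 0.99 | >0.99 |

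The entries are probabilities of a significant change. The documents give no recovery effect, so every shift is an assumption. Nothing comparable can be computed for VECTRA, because no SD is given.

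**6. Could Group C supply the time trend?** It has at most 20 patients, with a different operation and Breast-Q version. The detectable difference in change at 80% power is 2.80 × SD of change × √(1/83 + 1/20): 16.5, 14.0 and 10.8 points for r = 0.3, 0.5 and 0.7. All exceed the plan's 10-point difference of interest.

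**The case against.** The best defence is the opening of section 10.5. It says that confounding and within-patient correlation must be dealt with, and places all analyses in a mixed-model or GEE framework adjusting for W. The list for W is open-ended. Section 10.2 records radiation and chemotherapy details, and section 10.3 acknowledges the heterogeneity of treatment. A reader might infer from the one-line bullet that the plan commits to an unadjusted comparison. The documents do not say that; they leave the covariates unspecified. This part of the defence stands.

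It does not rescue the attribution. W is described through age, obesity and stage, which cannot remove a trend that every patient shares over time. Chemotherapy could fall within W, but step 4 shows that adding it as a main effect would change nothing.

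A second defence is that the objective defines its own measure in parentheses as scores before and after radiotherapy, so perhaps only a description is meant. That is a fair reading of the measure, but the question is still worded as the impact of radiation, and nothing in section 10.5.2 limits the conclusion.

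Third, the size of the problem is assumed. The probabilities in step 5 are ordinary test power. At r = 0.5 a 2-point shift gives only 0.15. This stands: the table shows what could happen, not how large the bias is.

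Last, this is one of six secondary objectives in an observational study, and neither the primary models nor the sample size depends on it. That also stands, and it limits the weight of the point.

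**Conclusion.** The point holds as one of attribution. The planned contrast estimates the total change between two visits about 32-113 weeks apart. Within an arm that is irradiated by definition, that total cannot be divided between radiation and recovery. The chemotherapy part can be examined, because it varies between patients and is recorded. The conclusion rests on the visit windows in sections 6.5 and 6.6 and on Group A being BCT + XRT throughout. If some BCT patients turn out not to be irradiated, they could serve as a comparator, but the plan defines none.

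Two stronger readings should be resisted. A reader might infer that recovery will be reported as a radiation effect, in a known direction. The documents give neither a direction nor a size, and 0.61 is an illustration that depends on an assumed 5-point shift. A reader might also infer that covariate adjustment would cure the problem. It would not, because recovery and radiation coincide in every patient. The change is worth making and cheap, but it is not critical to the study.

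**What to change.** In section 10.5.2:

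1. Name the estimate and its conclusion as *change from the early post-operative visit to after radiotherapy*, and stop describing it as the impact of radiation. This is the essential step.
2. Specify the plan's mixed model in BCT patients with visit, visit-by-chemotherapy between visits, and visit-by-weeks from lumpectomy to Visit 4. Say how a patient whose chemotherapy began before Visit 4 is coded. Main effects alone are not enough.
3. Report the change separately for patients with and without interval chemotherapy.
4. State that recovery cannot be fully separated from radiation in this arm.
5. For VECTRA outcomes, treated-minus-untreated breast differences may be added where the other breast was imaged and not operated on. They remove changes common to both breasts, but not swelling in the operated breast.

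The cost is a few sentences of analysis text, a more modest conclusion, and wider intervals for the chemotherapy-specific estimates. No extra patients or visits are needed; sections 6.6 and 10.2 already provide for recording treatment and timing.

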8.0 DATA SUBMISSION SCHEDULE

Case Report Form	Submission Schedule
Original Consent Form	Prior to registration
Eligibility Checklist RedCap Enrollment, Visit 1, Visit 2 MRI, and Visit 3 Plastics (if applicable)	Prior to surgery
RedCap Surgical Intervention	Following receipt of final operative and pathology reports
RedCap Follow-Up Forms Post-Operative Visit 1, Oncology Course, and Post-Operative Visit 2	
Group A:
 
 ○ Post-Lumpectomy 1st post-op visit before Radiotherapy (1-10 weeks after lumpectomy) ○ Post-Lumpectomy post-op visit after radiotherapy (6-18 months after radiation or the latest follow-up time point within the duration confines of our study period.) 
Group B:
 
 ○ Post-mastectomy 1st post-op visit before completion of reconstruction (1-10 weeks after mastectomy) ○ Post-mastectomy Post-op Visit after final reconstruction (3-8 months after final reconstructive procedure or the latest follow-up time point within the duration confines of our study period.) 
Group C:
 
 ○ Post-mastectomy 1st post-op visit (1-10 weeks after mastectomy) Post-mastectomy post-op visit (6-18 months after mastectomy or the latest follow-up time point within the

	duration confines of our study period.)
Unanticipated Event via HRPO	At the time of any unanticipated event
MRI T:B ratio, Breast Q-Scores, and Vectra Mammometrics	The coordinators will ensure MRI performed, Breast-Q's completed and Vectra images captured during active patient phase. MRI T:B ratio will be performed late in the active study phase to allow for a limited number of staff to perform bulk of measurements to optimize standardization. There is also a possibility the software will be upgraded to automate the T:B ratio later in the study period. Breast-Q scores and Vectra mammometrics will be also evaluated in bulk late in the active study phase using SAS, SPSS, or another similar statistical program.

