10.2 Data Fields Recorded

- PATIENT VARIABLES: BMI, smoking history, patient age, race, previous history breast augmentation,
- CANCER VARIABLES: cancer stage, presence or absence of sentinel lymph node biopsy, receptor status, tumor location, multifocal
- RADIATION & CHEMOTHERAPY VARIABLES: radiation received, length of treatment, chemotherapy selected, complications causing radiation or chemotherapy delay or dose reduction
- BREAST VARIABLES: standardized breast measurements (sternal notch to nipple, IMF to nipple, maximum areolar diameter, ptosis)
- SURGICAL VARIABLES: patients undergoing mastectomy with reconstruction as per routine will be recorded as immediate implant, expander-reconstruction, use of acellular dermal matrix, or flap including predominantly DIEP, but also free TRAM, latissimus, PAP, SIEA, TUG, or SGAP. Also balancing procedures will be considered like breast reduction/lift/augmentation/augmentation with lift, fat grafting, adjacent tissue transfer, pseudohernia repair, correction of malposition, implant exchange, capsulectomy, capsulorrhaphy, Ryan procedure,
- IMAGING VARIABLES: tumor: breast ratio, mammometrics (breast volumes, surface area, nipple position, chest wall morphology, vectors, anatomic landmarks)
- COMPLICATION VARIABLES: complications related to breast surgery will be recorded (anesthetic complications, bleeding, infection requiring readmission or surgery, wound healing problems requiring surgical intervention, need for re-excision in lumpectomy due to positive margins, and reconstructive failures due to flap loss or breast prosthesis explant). Patients with complications will be included as this is a key determinant of patient reported outcomes.

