10.5 Data Analysis

This is a longitudinal observational study to compare effects of two treatment groups on the quality of life and to explore how the treatment effects are modified by T:B ratio. For each study patient, we have a data vector $D=(\text{group}, \text{T:B ratio}, \text{location}, Q(t), 3D(t), W)$, where group is a binary indicator for two comparison groups. T:B ratio is the tumor: breast ratio measured at a continuous scale, and location is a binary indicator of tumor location. $Q(t)$ and $3D(t)$ are Q score and the VECTRA 3D generated mammometrics respectively, measured as continuous variables at $t=(0,1,2)$, where $t=0$ is the pre-treatment baseline measurement. W is a set of patient characteristics – e.g., age, obesity, stage, etc. A longitudinal study generates correlations among the repeated measurements within the same individual, and observational study often comes with a biased estimate of the treatment comparison due to confounding. These two issues, the correlation of repeated measurements and confounding, must be taken into account in the data

analysis. Regression analyses of correlated data can simultaneously address these two issues. There are two families of statistical methods for regression analyses of correlated data – mixed effect model and generalized estimating equation (GEE). Both are appropriate for our study, even though the interpretations are different – population average vs subject specific. Data analyses for our study will be performed within this framework to adjust for the patient characteristics for unbiased comparison of treatment effect and to take into account the correlations.

10.5.1 Primary objectives:

For main effect of treatment group on Q-score: fit and test a model with Q score as the dependent variable and group as the independent variable, controlling for W in the model – (Model 1).

For the difference in Q score between two treatment groups modified by T:B ratio: fit and test a model with Q score as the dependent variable, and group, T:B ratio, and group-by-T:B ratio interaction as the independent variables, controlling for W in the model – (Model 2). The results can be better presented as a graph with two lines – Q score as a function of T:B ratio for those treated with BCT, and for those treated with Mastectomy+reconstruction.

10.5.2 Secondary objectives:

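### The complications model in 10.5.2 leaves baseline Q, visit and event timing unstated; fitted over all three visits with a fixed indicator, it can misreport the loss and waste power

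*Combined protocol and SAP*

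**What the plan says.** Section 2.2 gives complications their own secondary objective: "How do complications that arise from each scenario (mastectomy + recon) vs. BCT impact patient satisfaction". Section 10.2 lists the events (anesthetic complications, bleeding, infection, wound problems, re-excision, flap loss, explant) and adds: "Patients with complications will be included as this is a key determinant of patient reported outcomes". Neither 10.2 nor 7.1 sets a time window or links an event to a visit.

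Section 10.5 describes Q and the mammometrics as "measured as continuous variables at $t=(0,1,2)$, where $t=0$ is the pre-treatment baseline measurement". It sets the analyses in a mixed-model or GEE framework: "Data analyses for our study will be performed within this framework to adjust for the patient characteristics". W is described as age, obesity, stage and similar characteristics. Baseline Q belongs to the outcome vector and is not named in W.

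The complications bullet in 10.5.2 reads: "Fit and test a model with Q-score as the dependent variable and complication and group, and possible group-by-complication interaction as independent variables", controlling for W. It does not say whether the indicator is fixed or time-varying, which visits enter, or how baseline Q is used. The radiation bullet in the same list does refer to time: "Perform the subgroup analyses of BCT patients comparing change in outcomes of interest before and after radiation".

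**The concern.** The listed complications follow from surgery and cannot change a score taken before it. If the bullet is fitted as its terms are listed, on the outcome that 10.5 defines, one patient-level coefficient averages the effect over three visits, and at one of them the effect is zero by construction.

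A complication after visit 4 also cannot affect t=1. Visit 4 falls 1-10 weeks after surgery, and in Group B before reconstruction is complete. Section 6.6 notes that reconstruction may be staged. In Group A, visit 5 is "6- 18 months after radiation or the latest follow-up time point within the duration confines of our study period". Late events are therefore possible in both arms.

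Without baseline adjustment, any pre-existing difference in Q between patients who do and do not go on to have complications also enters the coefficient. A true loss at the plan's own 10-point threshold could be reported as clearly smaller, or a baseline difference could be read as harm from complications.

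**Working it through.** **Inputs from the documents.** 83 patients per arm (166 in the two main arms), SD 20 and a 10-point meaningful difference, all from 10.4. The plan gives no figure for the complications model. Its 83 per arm can be reproduced: d=0.45, two-sided 0.05 and 80% power give 79 per arm for a t-test, and 79 × π/3 = 82.7, so 83 for a Wilcoxon-Mann-Whitney test with normal data.

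**Assumptions (the documents give none of these).** 20% complications, correlation 0.5 between any two visits, a loss that lasts, complete visits, and a share L of events after visit 4.

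**1. Fixed indicator over t=0, 1, 2.** With equal visit weights the coefficient is the mean effect over visits. An early event contributes (0+10+10)/3 = 6.67 and a late one (0+0+10)/3 = 3.33, so the reported loss is 10 × [(1−L)×2/3 + L×1/3].

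| L | Reported loss |
|---|---|
| 0 | 6.67 |
| 0.25 | 5.83 (5.9 in simulation) |
| 0.5 | 5.00 |
| 1 | 3.33 |

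A random-intercept model and an exchangeable GEE gave the same estimates, with or without a visit main effect in the mixed model.

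**2. Power.** With 20% of 166 affected, √(1/33.2 + 1/132.8) = 0.194.

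- Fixed indicator, three visits: the variance of a patient's mean is 400×(1+2×0.5)/3 = 266.7, SD 16.33, SE 3.17. At L=0, 6.67/3.17 = 2.10, power about 56%. At L=0.25, 5.83/3.17 = 1.84, power about 45%. Simulation: 55% and 45%.
- Post-operative mean with baseline Q as covariate, L=0: variance 300 − 200²/400 = 200, SD 14.14, SE 2.74, 10/2.74 = 3.64, power about 95%. Simulation: 94%, and also 94% at L=0.25 once events are dated.
- Post-operative mean without baseline Q, L=0: variance 400×(1+0.5)/2 = 300, SD 17.32, SE 3.36, 10/3.36 = 2.98, power about 85%. Simulation: about 82%.

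**3. Post-operative scores only, undated events.** There is no t=0 dilution, but a late event still averages to 5 over the two visits. At L=0.25 this gives 0.75×10 + 0.25×5 = 8.75.

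**4. Baseline gap.** Suppose patients with complications already score 5 points lower before surgery, a difference that persists and that W does not explain. At L=0 the fixed indicator gives 6.67 + 5 = 11.67; with a 5-point higher baseline it gives 6.67 − 5 = 1.67. A model with baseline Q as covariate is also off, but less so: the slope on baseline is 0.5, so 10 ± 5×(1−0.5) = 12.5 or 7.5. The within-patient contrast of t=2 with t=0 stays at about 10. Its SE is 20×0.194 = 3.88 and its power about 73% (about 72% by simulation).

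**5. Where the shortfall comes from at L=0.25.** The loss is 5.9 as read, 8.7 (power 87%) once baseline becomes a covariate, and 10.0 (94%) once events are also dated. The baseline step accounts for (8.7−5.9)/(10−5.9), about 70%.

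**6. Sensitivity.** For power at 25% late, fixed indicator against the fix:

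| Change | Fixed | Fix |
|---|---|---|
| 10% complications | 26% | 74% |
| 30% complications | 56% | 99% |
| correlation 0.3 | 54% | 91% |
| correlation 0.7 | 39% | 99% |

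In the setting kindest to the plan (30% complications, correlation 0.3, none late) power is 76% against 97%. The visit weights also depend on assumptions. AR(1) correlation 0.5 gives 60% of the loss for early events and 40% for late ones. A model that allows unequal variances gives 33% (baseline SD 15) or 88% (baseline SD 25) for early events.

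**The case against.** The strongest reply is that 10.5.1 and 10.5.2 name the terms of interest and are not full design matrices. None of the numbered models names a visit term, though the section calls the study longitudinal and t=0 the baseline. An analyst could use post-operative Q only or a time-varying indicator without contradicting the text. The objective concerns satisfaction, and 6.1 describes separate pre- and post-operative modules, so a chosen domain might have no pre-operative score. This stands as a limit on the size of the problem, but does not remove it: undated events still dilute the estimate, and where a pre-operative score exists, omitting it costs power.

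A reader might infer that the plan will report one-third to two-thirds of the true loss. The documents do not support that. The range needs a fixed indicator, t=0 as an outcome, equal weights, complete data and no baseline gap, and the plan states none of these. The one-third end needs every event to fall after visit 4. Bleeding and anesthetic complications are mainly early, and Appendix A (footnote 5) places visit 4 after margins are cleared, so re-excision comes first.

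The 94% is also a favourable figure, because the data were simulated with a lasting loss, as the dated model assumes. Checks that lean less on that assumption gave 84% at L=0.25 (visit 5 only, with baseline) and about 70-72% (complication-by-visit at t=2). With no baseline gap the fixed-indicator test keeps its type I error. The plan claims no power for this objective.

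**Conclusion.** The concern holds as under-specification that affects the result. On the fixed-indicator reading, with equal visit weights, complete data and equal baseline Q, a lasting 10-point loss appears as about 6.7 with no late events and about 5.9 with 25% late. Power is about 45-55% against about 94%, at an assumed 20% complications and correlation 0.5. On the post-operative-only reading the cost is about 8.8 of 10 at 25% late, and about 82% against 94% power with none late.

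Two stronger inferences should be resisted. The error is not always an understatement: a 5-point lower baseline gives about 11.7 and a 5-point higher one about 1.7. Nor is either arm shown to be favoured, since both can have early or late events and their timing is unknown.

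It would also be wrong to assume that the primary analysis escapes. Model 1 in 10.5.1 has the same form (Q on group and W, with no visit or baseline term) and the same issue on this reading.

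This is a secondary objective in an observational study, so the change is one that should be made rather than one on which the study depends.

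**What to change.** Replace the complications bullet in 10.5.2 with a mixed model of Q at t=1 and t=2 on baseline Q, visit, group, group-by-visit, C(t), C(t)-by-group and W. Set C(t)=1 only if a complication listed in 10.2 occurred before that assessment, otherwise 0. Name the Breast-Q domain. Report the loss in each arm with its 95% CI whatever the interaction p-value. In the 25%-late setting the interaction half-width is about 11.1 points and the single-arm half-width about 7.8.

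Also require the complication-by-visit contrast against t=0. It stays at about 10 under a baseline gap, where the C(t) model gives about 12.5 or 7.5, and it would show a loss that fades.

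Fallbacks: if baseline Q is missing for some patients, keep Q(0) in the outcome with C(0)=0 for everyone (same result in simulation). If dates cannot be recovered, use baseline Q as a covariate with a fixed indicator. State the visits and baseline handling for Model 1 at the same time.

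Event dates can come from the medical records already reviewed under 7.1 and the forms in 8.0 ("RedCap Follow-Up Forms Post-Operative Visit 1, Oncology Course, and Post-Operative Visit 2"). No new visits or patients are needed. The costs are slightly more abstraction, the C(t) model's assumption that the loss persists, and a less precise complication-by-visit contrast (power about 72%). If half the loss from early events has gone by visit 5, with 25% of events late, C(t) returns 8.1 and the fixed indicator 4.6.
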